### 3.1.1 RANDOMIZATION AND BLINDING

#### 3.1.1.1 RANDOMIZATION PROCEDURES

This is a double-blind, randomized, controlled trial with 2 groups: vaccine and placebo. The ratio of vaccine to placebo recipients is 5:1.

This seamless design has the block randomization conducted with age group as the stratification factor for both phase 2 and phase 3, having two levels of stratification. The two age groups are:

1. 18-45 and
2. 46-60.

Block randomization for Phase 3 involves site as an additional stratification factor i.e., Phase 3 will be conducted at two sites i.e., District Health Center of Ben Luc in Long An province and District Health Center of Long Thanh in Dong Nai province.

Each participant will be assigned a unique screening number assigned by the investigator after signing the informed consent. After an individual is determined to be eligible for study participation, the participant will be randomized according to age group by assigning a unique participant identification number sequentially in ascending order from the randomization schedule, which will contain the unique participant identification number and the corresponding randomization assignment and will be produced using computer software prior to the initiation of the study.

Once a participant identification number has been assigned to a participant, it will not be used again. Additional participants may be randomized into the study at the discretion of the sponsor in the case of any participant who is randomized but does not receive any study vaccine.

#### 3.1.1.2 BLINDING AND UNBLINDING PROCEDURES

The randomization will be conducted by an organization or individual not involved in the conduct of the study.

The randomization lists for participants will be used by IVAC to label study vaccine and placebo vials and then will be immediately sealed. It will be opened only after the clinical trial database is declared complete and locked. In the case of any unblinding, researchers must report this in writing to the overseeing Ethics Committee.

Study product injected into each participant will be recorded on the electronic Case Report Form (eCRF) using the exact allocation code for each product received by each participant. The allocation codes link treatment identification with each participant via participant identification numbers. These will be maintained in a secure location, by an individual not involved in the conduct of the study. If any participant experiences an SAE possibly related to receipt of study treatment and the investigator determines it is necessary to unblind, treatment allocation to the participant may be communicated to the investigator.

---

Document:	\\EEDC-NAS01A\Biosdata\Path\IVACFLU-S\IYA06804\Biostatistics		
	Documentation\SAP\IVACFLU-S-0203_SAP_Draft v1.0		
Author:	[name]	Version Number:	1.0
		Version Date:	[11AUG2017]
Template No:	CS_TP_BS016 Revision 4	Reference:	CS_WI_BS005
Effective Date:	01Apr2016		

A blinded dummy randomization schedule was produced for blinded statistical programming purposes.

An example of the schedule structure is given in Table 1.

Table 1: Example structure of randomization schedule.

Protocol Identifier	Schedule Type	Phase	Site	Age group	Block Number	Randomization Number	Kit Identifier	Randomized Treatment Group	Numeric Randomized treatment group	Overage
IVACFLU-S-0203	Actual_u	2	Long An	18 – 45 years of age	XX	A001	A001	IVACFLU-S	1	No
...	...				...	...	...	...		
IVACFLU-S-0203	Actual_u	2	Long An	18 – 45 years of age	XX	A126	A126	PLACEBO	2	No
...	...				...	...	...	...		

### 3.2 SCHEDULE OF EVENTS

Schedule of events can be found in [Table 2](#).

Document: \\EEDC-NAS01A\Biosdata\Path\IVACFLU-S\IYA06804\Biostatistics  
 \Documentation\SAP\IVACFLU-S-0203\_SAP\_Draft v1.0  
 Author: [name]  
 Version Number: 1.0  
 Version Date: [11AUG2017]  
 Template No: CS\_TP\_BS016 Revision 4  
 Effective Date: 01Apr2016  
 Reference: CS\_WI\_BS005

Table 2: Schedule of events of the protocol synopsis of Protocol IVACFLU-S-0203, Phase 2/3, version 4.0 dated 09Feb2017.

Study Activities	Study Day (# days from D1)					
	S1/D1* (up to -4/ D1 Clinic Visit	D1 to D7	D8 (+/- 1) Clinic Visit	D9 to D21	D22 (+/- 1) Clinic Visit	D91 (+/- 7) Telephonic contact
Information process and written informed consent	X					
Collect baseline demographic data	X					
Collect/review medical history	X					
Perform screening physical examination	X					
Perform vital signs & targeted physical examination (symptom based & reactogenicity only)	X*		X			
Perform urine pregnancy check (women)	X*					
Check/confirm inclusion/exclusion criteria	X*					
Randomization	X					
Collect serum for influenza serology	X**				X	
Administer one dose of study product (vaccine or placebo)	X					
Observe for 30 Minutes; record and manage immediate reactions	X					
Instruct participant on use of Dairy card	X					
Participant records solicited reactogenicity and unsolicited AEs in Diary cards	X	X				
Clinical staff reviews interim AEs/SAEs with participant; records in CRF			X		X	SAE only
Report SAEs to Sponsor, IRBs and regulatory authorities	X	X	X	X	X	X
Participant completion of study						X
*If Day 1 is conducted on a different day from S1, eligibility must be confirmed again on Day of Injection (D1); including Targeted physical examination (PE); inclusion/exclusion; urine pregnancy test. ** Sera samples will be collected prior to vaccination in phase 3 study at one site (Ben Luc).						

### 3.3 CHANGES TO ANALYSIS FROM PROTOCOL

No changes to planned analyses in the protocol will be applied.

Document: \\EEDC-NAS01A\Biosdata\Path\IVACFLU-S\IYA06804\Biostatistics  
Documentation\SAP\IVACFLU-S-0203\_SAP\_Draft v1.0

Author: [name]

Version Number:

1.0

Version Date:

[11AUG2017]

Template No: CS\_TP\_BS016 Revision 4  
Effective Date: 01Apr2016

Reference: CS\_WI\_BS005

Copyright © 2009, 2010, 2012, 2016 Quintiles Transnational Corp. All rights reserved.

The contents of this document are confidential and proprietary to Quintiles Transnational Corp. Unauthorized use, disclosure or reproduction is strictly prohibited.

## 4 PLANNED ANALYSES

The primary focus of this SAP is to describe safety analyses that will be conducted on the combined Phase 2 and Phase 3 data, as well as the immunogenicity analyses that will be conducted on the Phase 3 data.

### 4.1 DATA AND SAFETY MONITORING BOARD

Given the wide global experience with seasonal influenza vaccines and the safety profile observed in the Phase 1 study, there will not be any Data Safety Monitoring Board (DSMB) for this study. The PSRT will be responsible for close safety oversight of the study.

### 4.2 INTERIM ANALYSIS

Blinded safety data up to Day 8 for Phase 2 subjects will be analysed and reviewed by the PSRT team. In addition, all grade 3 and above unsolicited AEs and SAEs until the data cut-off date will also be part of an interim report. This report will be submitted to the Pasteur Institute Ho Chi Minh City Institutional Review Board (IRB) and Vietnam Ministry of Health (MOH) for review and approval before initiating the Phase 3 study.

### 4.3 FINAL ANALYSIS

Analyses will be conducted only after all related data have been entered, cleaned, locked and the study datasets routinely unblinded. Given the short duration of clinical follow-up and potential delays in generating immunogenicity results, analysis of safety and immunogenicity data will be conducted independently. All final, planned analyses identified in this SAP will be performed by QuintilesIMS Biostatistics following:

1. Sponsor authorization of the analysis sets;
2. Sponsor authorization of the final SAP and Tables, Listings and Figures (TLF) Shells;
3. Authorization of data issues log;
4. Authorization of data handling report;
5. Database lock;
6. Routine unblinding of study datasets for analysis; and
7. Identification of treatment deviations (randomized versus actual).

## 5 ANALYSIS SETS

Agreement and authorization by the sponsor of subjects included/excluded from each analysis set will be conducted prior to the unblinding of the study data.

---

Document:	\\EEDC-NAS01A\Biosdata\Path\IVACFLU-S\IYA06804\Biostatistics		
	Documentation\SAP\IVACFLU-S-0203_SAP_Draft v1.0		
Author:	[name]	Version Number:	1.0
		Version Date:	[11AUG2017]
Template No:	CS_TP_BS016 Revision 4	Reference:	CS_WI_BS005
Effective Date:	01Apr2016		

## 5.1 ENROLLED POPULATION

All screened subjects who are randomized, regardless of the subject's randomization and treatment status in the trial.

## 5.2 FULL ANALYSIS [FA] POPULATION

All subjects in the enrolled population who were randomized and received a study vaccination. This population will serve as the primary analysis population for all safety objectives. The analysis based on this population will serve as the supportive results for all safety objectives. Subjects will be analyzed as randomized.

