#### Full Analysis (FA) Population

All participants in the enrolled population who were randomized and received a study vaccination. This population will serve as the primary analysis population for all safety objectives. The analysis based on this population will serve as the supportive results for all safety objectives. Participants will be analyzed as randomized.

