### 17.2.1.2 PRESENTATION OF SOLICITED LOCAL AND SYSTEMIC ADVERSE EVENTS

The following will be presented for the FA population:

1. Subject-wise listing of solicited local and systemic adverse events will be generated separately.
2. Summary of solicited local and systemic adverse events will be provided separately as follows:
  - Counts and percentages of subjects experiencing each reaction or event, at least one reaction or event will be calculated.
  - Number of events for each reaction or event will also be displayed.
  - Event will be counted only one time if occurred on consecutive days.

Percentages of participants experiencing each reaction or event, or at least one reaction or event will be calculated along with two-sided exact 95% CIs using Clopper-Pearson method (refer [Appendix 2](#)) for each treatment group and by age group. Fisher's exact test (refer [Appendix 3](#)) or Cochran-Mantel-Haenszel test (refer [Appendix 4](#)) will be used to compare the proportion of participants between the two treatment groups.

3. Summary of solicited local and systemic adverse events, as described in the above point 2 will be repeated i.e., summarized by day:

---

Document:	\\EEDC-NAS01A\Biosdata\Path\IVACFLU-S\IYA06804\Biostatistics		
	Documentation\SAP\IVACFLU-S-0203_SAP_Draft v1.0		
Author:	[name]	Version Number:	1.0
		Version Date:	[11AUG2017]
Template No:	CS_TP_BS016 Revision 4	Reference:	CS_WI_BS005
Effective Date:	01Apr2016		

- Counts and percentages of subjects experiencing each reaction or event, at least one reaction or event will be calculated.
  - Number of events for each reaction or event will also be displayed.
4. Descriptive summary (as described for continuous variables in [Section 6](#)) of the size of the solicited local reactions captured as per the eCRF will be presented by vaccine and placebo.

In addition, for all Solicited Local and Systemic Adverse Events the following will be summarised by maximum severity until resolution:

- Counts of all events will be reported and summarized, as “any local AE” or “any systemic AE”.
- Percentages of subjects experiencing each reaction or event, at least one reaction or event will be calculated. This will be generated separately i.e., one output for Body temperature (Oral) and one output for all other adverse events, as the severity grades will be as follows:
  - Body temperature (Oral):
    - Ungradable
    - Grade 1= ‘38.0 - <38.6°C’
    - Grade 2= ‘38.6 – <39.3°C’

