### Protocol Deviation Classifications

Categories	Severity

 
• Informed consent
 
• Eligibility and Entry Criteria
 
• Concomitant Medication Criteria
 
• Study Procedures Criteria
 
• Serious Adverse Event Criteria
 
• Randomization Criteria
 
• Visit Schedule Criteria
 
• Administrative Criteria
 
• Source Document Criteria
 
• RA or CEC Approvals Criteria
 
• IP Compliance
 
• Other Criteria
 
	
 
• Minor Deviations from accepted procedures that will not adversely affect subject/data, but should be dealt with appropriately.
 
• Major Protocol Deviation Issues that impact upon scientific, ethical, regulatory or business integrity and which, if left unattended could become critical. Such issues require timely action.
 
• Critical Protocol Deviation Issues that threaten scientific, ethical, regulatory or business integrity and could invalidate acceptability of a study (or part of it) to a customer or regulatory body, or invoke regulatory action which require immediate attention.
 

**Critical** deviations include, but are not limited to:

- Eligibility and entry criteria: subject was enrolled even though entry criteria were not satisfied
- Subject did not sign ICF yet was enrolled into the study
- Any study procedures on S1 day were done prior to consent being signed

**Major** deviations include, but are not limited to:

- Incorrect study product assigned and administered according to randomization
- Incorrect version of signed ICF (not currently approved version)
- ICF was not signed by either investigator or study participant
- IP temperature excursion (important deviation if IP is not allowed to be used, minor deviation if IP is allowed to be used)
- Subject does not complete more than 50% of subject diary card
- Subject visit (D8, D22, D91) is not completed or not done Use of prohibited drugs during study period
- SAE not reported according to protocol requirement
- Immunological sample is not collected as per protocol requirement (collected sample which cannot be analyzed is not considered as a deviation)
- Loss of source documents

**Minor** deviations include, but are not limited to:

- Subject visit is outside of visit window
- Incomplete source documents
- Procedures carried out by staff not delegated in the delegation log

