NOTE: in eCRF is Product Code which means that we will be able to check "actual" treatment. We have the RND number so we can check RND treatment if not as part of DS then at least here we need to show actual and randomized treatment and flag any deviations. Also please ensure this is clarified in the SAP.

Programming Note: Sort by Actual Treatment, Subject ID and Visit.

Document: \\IEEDC-NAS01A\Biosdata\Path\IVACFLU-S\IYA06804\Biostatistics \Documentation\SAP\IVACFLU-S-0203\_Mock\_Listings\_V1.0  
 Author: [name]  
 Version Number: 1.0  
 Version Date: [11AUG2017]

Template No: CS\_TP\_BS016 Revision 4  
 Effective Date: 01Apr2016

Reference: CS\_WI\_BS005

Copyright © 2009, 2010, 2012, 2016 Quintiles Transnational Corp. All rights reserved.  
 The contents of this document are confidential and proprietary to Quintiles Transnational Corp. Unauthorized use, disclosure or reproduction is strictly prohibited.

TABLE AND LISTING MOCK SHELL

Listing 16.2.6.1  
 Immunogenicity Result  
 Per-Protocol Population

Treatment	Subject ID/ Site ID/Age Group	Visit	Collection Date/Study Day	Antigens	HAI			
					Titer	Fold Increase (Day 22/Day 1)	>=1:40 Titer (Yes/No)	Seroconversion (Yes/No)
Vaccine	xxxxx/ xxxx/ xxxx	Day 1	DDMMYYYY/ xx	H1N1	xx	xx	Yes	Yes
		Day 22						
	xxxxx/ xxxx/ xxxx							
	xxxxx/ xxxx/ xxxx							

HAI: Hemagglutination Inhibition

Study day: Derived relative to administration date/time of vaccination.

Seroconversion is defined as a serum HAI antibody titer meeting the following criteria:

- Pre-vaccination titer <1:10 and a post-vaccination titer measured on Day 22 of ≥1:40 or
- Pre-vaccination titer ≥1:10 and at least a four-fold increase in post vaccination measured on Day 22

Programming Note: Sort by Treatment, Subject ID and Visit.

Document: \\IEEDC-NAS01A\Biosdata\Path\IVACFLU-S\IYA06804\Biostatistics \Documentation\SAP\IVACFLU-S-0203\_Mock\_Listings\_V1.0  
 Author: [name]  
 Version Number:  
 Version Date:

1.0  
 [11AUG2017]

Template No: CS\_TP\_BS016 Revision 4  
 Effective Date: 01Apr2016

Reference: CS\_WI\_BS005

Copyright © 2009, 2010, 2012, 2016 Quintiles Transnational Corp. All rights reserved.

The contents of this document are confidential and proprietary to Quintiles Transnational Corp. Unauthorized use, disclosure or reproduction is strictly prohibited.

TABLE AND LISTING MOCK SHELL

Listing 16.2.6.2  
 Immunogenicity Result- Antigens  
 Per-Protocol Population

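### Safety is tabulated only by randomized arm, so a participant given the other arm's product would have reactions and SAEs counted under the product not received

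*Combined protocol and SAP*

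**What the plan says.** Protocol 13.6 and SAP 5.2 define three sets: Enrolled, Full Analysis and Per Protocol. Per Protocol serves immunogenicity, so FA (randomized and vaccinated) is the only set used for safety. The rule for FA is "Participants will be analyzed as randomized" in the protocol and "Subjects will be analyzed as randomized" in the SAP. SAP 3.3 adds "No changes to planned analyses in the protocol will be applied", so the two documents agree.

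SAP 17.2 places the 30-minute, Day 1 to 7, unsolicited and serious event outputs on this set. Section 17.2.1.2, for example, opens with "The following will be presented for the FA population". The 14.3 table shells have Vaccine and Placebo columns on the FA population, with no version or footnote by product received.

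The SAP does foresee a mismatch. Section 4.3, step 7, is the identification of treatment deviations, randomized against actual. Appendix 1 lists as a major deviation "Incorrect study product assigned and administered according to randomization". The note on the shell for Listing 16.2.5 says "here we need to show actual and randomized treatment and flag any deviations", followed by "Also please ensure this is clarified in the SAP". No SAP section then says what actual treatment is used for beyond being identified and listed.

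**The concern.** Safety is a primary objective in both phases, and its question is what happens to people who receive the vaccine. SAP 17.1 states its precision in those terms: no related SAE among 700 vaccine recipients excludes a rate of about 0.43%. Under the FA rule the vaccine column counts people randomized to vaccine. The two groups differ in exactly the situation that step 7 and Appendix 1 anticipate.

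After a cross-arm error, tabulation by randomized arm pulls the two arms' reaction rates together and can put a vaccine recipient's SAE in the placebo column. For a safety comparison, dilution errs in the reassuring direction. Immunogenicity has a fallback, because Per Protocol can drop violations that interfere with the assessment. Safety has none. Step 7 also follows unblinding, so a response improvised then would be chosen with allocation known.

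**Working it through.** **The plan's own precision figures (SAP 17.1, Table 7; n = 700).**
- Upper bound with no events, one-sided 95%: 1 − 0.05^(1/700) = 0.427%. The plan says about 0.43%.
- Probability of at least one event, 1 − (1 − p)^700: 90.1% at p = 0.33% and 95.1% at p = 0.43%. The plan says 90% and over 95%.
- Two-sided exact upper limits for 0 and 1 event: 0.526% and 0.793%. Table 7 prints 0.52 and 0.79, consistent with truncation.

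The figures reproduce.

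**Denominators (protocol Table 15).** Placebo: 42 in Phase 2 + 106 in Phase 3 = 148; per age group 21 + 53 = 74. Vaccine: 888 − 148 = 740.

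**Common reactions, one crossed participant.**
- Placebo-randomized, given vaccine: the placebo rate moves by at most 1/148 = 0.68 points, or 1/74 = 1.35 points in one age group.
- Vaccine-randomized, given placebo: the vaccine rate moves by at most 1/740 = 0.14 points.
- Expected shift of the placebo rate, using the Phase 1 Day 1 rates for any local reaction (20/30 vaccine, 8/30 placebo; protocol 2.1.6): the difference is 0.40, so 0.40/148 = 0.27 points, or 0.40/74 = 0.54 points in one age group.

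**Rare events.** Assume one placebo-randomized participant is given vaccine and has the only related SAE in the trial. Exact one-sided 95% upper bounds for the vaccine column:

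| Tabulation | Vaccine | Upper bound | Placebo |
|---|---|---|---|
| As randomized | 0/740 | 0.40% | 1/148 |
| By product received | 1/741 | 0.64% | 0/147 |

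On the plan's n = 700 the one-sided contrast is 0.43% (0 events) against 0.68% (1 event).

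**How likely is that case?** Given one such cross-over, and a related-SAE rate p per vaccine recipient, the probability that this person has the SAE and none of the other 740 does is p(1 − p)^740:
- p = 0.33%: about 0.03%
- p = 0.43%: about 0.02%
- largest possible value, at p = 1/741: about 0.05%

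**Which dispensing errors matter?** A wrong vial of the same product has no effect. Assuming a wrong vial is drawn at random in the 5:1 ratio, (25 + 1)/36 = 72% of errors give the same product, and 5/36 = 14% give vaccine to a placebo participant.

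**The case against.** The strongest reply is that this is hypothetical and small. Nothing changes without a cross-over, and the safeguards are sound: kit numbers equal randomization numbers, vials are labelled from the randomization list, the injector confirms the product, the vial number is recorded, empty vials are kept until monitors have verified that they may be discarded, and monitors check that randomization was followed. The SAE contrast needs several unlikely things at once. For common reactions an expected shift of 0.27 points is trivial against a 40-point Phase 1 difference. No numerical safety criterion depends on the tables, and unsolicited events and SAEs are not tested.

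A cross-over would also be visible, in the deviation table and in Listing 16.2.5. The shell note asks for display and flagging rather than as-treated tables, so step 7 and Appendix 1 may be read as the clarification it sought. Finally, decoding the product code cannot detect wrong contents in a correctly numbered vial.

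All of this stands as a limit on weight, and the note is only weak evidence that the point was left open. None of it alters the rule. A listing lets a reader trace a case by hand, but the arm totals, intervals and p-values remain by randomized arm, and the AE and SAE listings have a Treatment column that does not say which treatment it means.

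**Conclusion.** The concern holds. Both documents commit all safety tables to the randomized arm, and the actual treatment that the SAP identifies corrects none of them. The rule itself gives wrong arm counts after a cross-arm error.

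The effect is contingent: zero with no cross-over, at most 0.68 points per misdosed placebo participant (1.35 within an age group), and potentially the difference between no related SAE and one in the vaccine column. The last case is very unlikely, but it bears directly on the statement in SAP 17.1. The sizes assume planned enrolment; the expected shifts also assume Phase 1 reaction rates. The documents give no error rate, so no overall probability can be stated. This is a change worth making because it costs almost nothing, not because a material distortion is expected.

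**What to change.** Tabulate all safety outputs, for participants who received study product, by the product actually received, decoded after unblinding from the study product code on the vaccination eCRF. Footnote each participant whose actual and randomized arms differ, and label the Treatment column in the AE and SAE listings. Keep FA as randomized for the supportive immunogenicity analyses in SAP 16.2.2.

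Make the change in protocol 13.6, or declare it as a departure in SAP 3.3, and carry it into SAP 5.2 and the shells. Fix it before unblinding. The cost is wording only: the code is already collected, and Listing 16.2.5 already shows actual treatment. Wrong contents in a correctly numbered vial would remain undetected.

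As an editorial matter, SAP 5.2 and protocol 13.6 call the FA analysis both primary and supportive for safety. This changes no table, but the two sentences should be reconciled in the same edit.
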